2.6.1 Dose modifications

2.6.1.1 Dose reductions (Parts 1-3)

Dose or schedule reduction for patients may be warranted after Cycle 1 as a consequence of drug-related toxicities. Dose reduction will be documented in the CRF along with reason for reduction. The decision to reduce the dose will be made by the Investigator, who may consult with the Sponsor if indicated.

At a starting dose level of 18 mg/m²/day, no dose reduction is anticipated for patients in the first cohort. If unacceptable toxicity occurs in a patient, then that patient will be instructed to stop treatment.

Patients with toxicities that are manageable with supportive therapy may not require dose reductions (e.g., nausea/vomiting may be treated with antiemetics). Patients with toxicities up to Grade 3 that are clinically tolerable in the Investigator's opinion may not require dose reductions (e.g. severe diarrhea of short duration).

For adverse events not specified below, doses may be reduced or held at the discretion of the investigator for the patient's safety. The sponsor should be made aware of such reductions.

Suggested dose modifications based on type of AE or laboratory findings:

Grade 4 neutropenia or clinically intolerable Grade 3 neutropenia:

- First occurrence- hold TK216 until ANC $\geq 1,000/\text{mm}^3$, then resume TK216 at same dose and schedule.
- Second or subsequent occurrence- hold TK216 until ANC $\geq 1,000/\text{mm}^3$, then reduce TK216 daily dose to one dose level lower than the current dose.

Patients experiencing \geq Grade 2 neutropenia may receive G-CSF or other myeloid growth factors after the first cycle or as defined in the dose and schedule escalation plan.

Grade 4 thrombocytopenia or any clinically significant thrombocytopenic bleeding:

- First occurrence- hold TK216 until platelets $\geq 50,000/\text{mm}^3$, then resume TK216 at same dose and schedule.
- Second or subsequent occurrence- hold TK216 until platelets $\geq 50,000/\text{mm}^3$, then reduce TK216 dose to one daily dose level lower than the current dose.
- Use of platelet growth factors or platelet transfusions is permissible.

Hemoglobin ≤ 8.0 gm/dL

- Any occurrence- hold TK216 until hemoglobin ≥ 8.0 gm/dL, then resume TK216 at same dose. Blood transfusions are permitted.

Grade 3 or greater non-hematologic toxicity (unless clearly and incontrovertibly unrelated to TK216):

- Any occurrence- hold TK216 until toxicities have resolved or improved to Grade 2 severity levels, then resume TK216 at same dose if event was a tolerable Grade 3 (at PI's discretion). Reduce TK216 dose to one dose cohort level lower than the current dose if event is Grade 3 or 4 or intolerable Grade 2 in severity.

Vincristine dosing will be interrupted for any clinically intolerable neuropathy (e.g. grade 4 foot drop, severe paresis, disabling paresthesias or ileus), and may be resumed if the neuropathy becomes clinically tolerable. If seizures occur the vincristine dosing should be interrupted until seizure activity is controlled, and may be resumed if antitumor responses warrant in the opinion of the Investigator. In either case, the subsequent vincristine dose should be 0.75 mg/m². If the total bilirubin increases to greater than 1.9 mg/dL, vincristine dosing should be stopped. If the total bilirubin is between 1.5 – 1.9 mg/dL then vincristine should be

administered at 0.75 mg/m².

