It is anticipated that 4 to 6 cohorts will be completed during the schedule escalation segment of this trial. With the concurrence of the investigators and the study sponsor, further testing may be performed in up to 12 additional patients per dose level to refine the estimation of the MTD and RP2D at intermediate dose levels or to define a higher MTD and RP2D while using Cycle 1 primary supportive care prophylaxis (e.g., with growth factors, antidiarrheals, antiemetics) for bone marrow and/or gastrointestinal toxicities.

The duration of cycles will be variable. Following the scheduled infusions of TK216, a rest period will begin. The next cycle for a patient may begin as soon as all the patient's toxicities attributed to TK216 have resolved to less than Grade 3, or are clinically tolerable Grade 3 toxicities.

Once a patient completes Cycle 2 of any schedule escalation cohort, vincristine can be administered on Day 1 of a subsequent cycle and on Day 1 of each subsequent cycle. The initial dose of vincristine on Day 1 of the starting cycle will be 0.75 mg/m² given via intravenous infusion prior to the initiation of the TK216 infusion. Subsequent doses beginning on Day 1 of the next cycle and beyond will be 1.5 mg/m² up to a maximum dose of 2 mg.

Additional cycles of therapy may be administered provided that the patient meets the following criteria on Day 1 of each cycle:

- ANC \geq 1,000/mm³
- Hemoglobin \geq 8.0 gm/dL (Blood transfusions are permitted.)
- Platelets \geq 50,000/mm³
- Non-hematologic toxicity(s) recovered to less than Grade 3, or are clinically tolerable Grade 3 toxicities
- In patients receiving vincristine, clinically tolerable neurotoxicity, and lack of seizure activity

A rest period of 14 days is required following the first cycle, but the rest period may be reduced following subsequent treatments if the above criteria are met.

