6.3.6 Expansion Cohort (Cohort 10)

4.2.3.1 Expansion Cohort: On study Schedule (Cohort 10)

Patients enrolled in the Expansion Cohort will be assessed and treated the same as described for the Schedule Escalation Cohorts in Section 6.3.5, as applicable to the selected regimen.

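### Part 2 allows a new cycle with a tolerable Grade 3 non-hematologic toxicity still present, Section 2.6.1.1 holds TK216 until Grade 2, and nothing says which rule governs

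*Combined protocol and SAP*

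**What the plan says.** Section 2.3 (Part 2) addresses the start of the next cycle twice. The narrative lets it begin once all toxicities attributed to TK216 "have resolved to less than Grade 3, or are clinically tolerable Grade 3 toxicities". The Day 1 criteria further down repeat the allowance: "Non-hematologic toxicity(s) recovered to less than Grade 3, or are clinically tolerable Grade 3 toxicities".

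Section 2.6.1.1 applies, by its title, to Parts 1 to 3. Under the line "Suggested dose modifications based on type of AE or laboratory findings" it takes non-hematologic toxicity of Grade 3 or worse, unless clearly unrelated to TK216. At every occurrence the instruction is to "hold TK216 until toxicities have resolved or improved to Grade 2 severity levels", and "then resume TK216 at same dose if event was a tolerable Grade 3", at the investigator's discretion.

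Section 2.4 (Part 3) sets out dosing and infusion length but no criteria for starting a further cycle. Section 4.2.3.1 says that Cohort 10 patients "will be assessed and treated the same as described for the Schedule Escalation Cohorts" in Section 6.3.5, as far as this applies to the selected regimen.

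**The concern.** Both sections can apply to the same patient on the same day. A patient with a tolerable Grade 3 non-hematologic toxicity on the planned first day of a cycle can be infused at one site and held at another, and each site can point to the protocol.

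This is first a safety matter: whether a continuous infusion restarts while a Grade 3 toxicity is present, in cohorts open to patients from 10 years of age. It also bears on interpretation. Section 9 plans exploratory analyses by actual dose, days of treatment and cumulative exposure. Part of the variation in those quantities could reflect which section a site followed.

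**Working it through.** No sample size, power or event count is at issue, so there is no plan figure to reproduce. The check is to apply both rules to one test case.

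**Test case.** A Part 2 patient is due for the next cycle. Neutrophils, hemoglobin and platelets meet the Day 1 criteria. A non-hematologic toxicity is ongoing and attributed to TK216, so it falls within both sections.

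| State of the toxicity on planned Day 1 | Section 2.3 | Section 2.6.1.1 (event was Grade 3 or worse) | Agree? |
|---|---|---|---|
| Improved to Grade 2 or lower | may start | hold ends | yes |
| Grade 3, clinically tolerable | may start | hold | **no** |
| Grade 3, not tolerable | may not start | hold | yes |
| Grade 4 | may not start | hold | yes |

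The rules give opposite actions in one row only.

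**Can Section 2.6.1.1 be read so that the row disappears?**

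1. *As covering intolerable events only.* No. The bullet names the tolerable Grade 3 event, and uses tolerability only to choose the dose after the hold.
2. *As covering only events during an infusion.* The text sets no such limit; it speaks of every occurrence. The blood-count rules point the same way. The levels that release a hold in 2.6.1.1 (neutrophils 1,000/mm³, platelets 50,000/mm³, hemoglobin 8.0 gm/dL) are the same as the Day 1 levels in 2.3. Hold-release and cycle-start limits match for each blood count and part only for non-hematologic toxicity.
3. *As softened by the earlier sentence in 2.6.1.1 on tolerable toxicities up to Grade 3.* That sentence says they may not need a dose reduction. It does not mention holding the drug.

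**Does the DLT rule remove the patient?** No. Table 2 counts a Grade 3 non-hematologic toxicity as a DLT only when it is not clinically tolerable.

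**Part 1.** Section 2.2 requires recovery to Grade 1, or a tolerable Grade 2, before a further cycle. It has no allowance for tolerable Grade 3, so this conflict does not arise there.

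**Part 3.** The hold rule applies through the title of 2.6.1.1. To reach the Part 2 allowance, a reader must go from 4.2.3.1 to Section 6.3.5. That section lists visits and procedures and does not state the allowance. Its rest-period subsection, 6.3.5.8, refers for the criteria to resume to Sections 4.3 and 6.3.8.1, and neither number exists in the current text. The chain ends there.

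**The case against.** The best defense is that the two texts differ in force and purpose. Section 2.3 is a permission for starting a cycle. Section 2.6.1.1 offers suggestions, leaves the decision to reduce the dose to the investigator, and uses words such as hold and resume that fit an interruption better than the end of a rest period. A site that waits for Grade 2 breaches neither section; a site that starts departs only from a suggestion. It can also be argued that 2.6.1.1 uses the word reduction loosely enough to include holds, since one paragraph speaks of doses reduced or held and then calls both reductions. Tolerable Grade 3 would then be left to judgment throughout.

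This softens the conflict without removing it. The bullet is worded as an instruction, it deals with the tolerable Grade 3 event by name, and no sentence says that the Part 2 criteria override it.

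Three stronger readings are tempting, and the objection is right to resist them:

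- *That the conflict concerns Grade 3 toxicity in general.* It does not; the hold rule in question is for non-hematologic events, and the blood-count limits agree.
- *That it is equally explicit in Part 3.* It is not; the cycle-start allowance is written only in Section 2.3.
- *That it causes a calculable loss of dose intensity, or shifts scan dates and the response rate in Part 3.* Section 2.3 makes cycle length variable and fixes the 14-day rest only after the first cycle, so there is no standard cycle against which to measure a delay. Part 3 scans already follow cycles whose infusions may be lengthened from Cycle 3. The documents do not show that this wording adds materially to that variation.

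**Conclusion.** The contradiction stands, within narrow limits. In Part 2 it is explicit for an ongoing, TK216-attributed, clinically tolerable Grade 3 non-hematologic toxicity at the planned start of a cycle: Section 2.3 permits infusion, Section 2.6.1.1 holds it, and precedence is not stated. In Part 3 the defect is of another kind: the hold rule applies, but the cycle-start criteria cannot be found by following the references given.

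Its size cannot be stated. The documents give neither the number of patients likely to be in this state nor the time such a toxicity takes to improve, and the finding does not depend on either. It rests on reading the hold rule as written, without an unstated restriction to events during an infusion. It is worth correcting because it touches patient safety and consistency between sites. It does not call the planned efficacy analysis into question. The dose at which treatment resumes after a hold is a separate matter.

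**What to change.** Reconcile Sections 2.3 and 2.6.1.1:

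- State which section governs the start of a new cycle and which governs an event during an infusion.
- Where both apply, use the same grade limit for non-hematologic toxicity.
- In Section 2.4, state which cycle-start criteria apply to Part 3, and correct the references in 6.3.5.8 to Sections 4.3 and 6.3.8.1.

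The choice of clinical rule belongs to the sponsor and the investigators and is not proposed here. The cost is wording in these four places; no new data, assessments or patients are needed.

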2.6.2 Dose Reductions (Part 4)

Dose reduction for patients may be warranted as a consequence of drug-related toxicities. Dose reduction will be documented in the CRF along with reason for reduction. The decision to reduce the dose will be made by the Investigator, who may consult with the Sponsor if indicated.

- Cohort 11 dose is 175 mg/m²/day for 28 days.
 - First occurrence, wait for the AE to decrease to ≤ Grade 2 and then resume TK216 at same dose and schedule.
 - Second or subsequent occurrence of AE- hold the dose until AE ≤ Grade 2, and then reduce TK216 daily dose to 145 mg/m²/day. If a subsequent dose reduction is required, reduce TK216 daily dose to 130 mg/m²/day.
 - If a further dose reduction below TK216 daily dose to 130 mg/m²/day is required, discuss with Sponsor, as the patient may require discontinuation of TK216

Patients with toxicities that are manageable with supportive therapy may not require dose reductions (e.g., nausea/vomiting may be treated with antiemetics). Patients with toxicities up to Grade 3 that are clinically tolerable in the Investigator's opinion may not require dose reductions (e.g., severe diarrhea of short duration). If unacceptable toxicity occurs in a patient, then that patient will be instructed to stop treatment.

For adverse events not specified, doses may be reduced or held at the discretion of the investigator for the patient's safety. The Sponsor should be made aware of such reductions. If toxicities resolve at a lower dose level after one cycle, the investigator may adjust the dose upwards at their discretion.

Grade 3 or greater non-hematologic toxicity (unless clearly and incontrovertibly unrelated to TK216)

- Following any occurrence: hold TK216 until toxicities have resolved or improved to ≤ Grade 2 severity levels, then resume TK216 at same dose if event was a tolerable Grade 3 (at PI's discretion). Reduce TK216 dose to one dose level lower (145 mg/m²/day, 130 mg/m²/day) than the current dose if event is Grade 3 or 4 or intolerable Grade 2 in severity.

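### Section 2.6.2 gives two restart doses, 175 and 145 mg/m²/day, after a first Grade 4 or intolerable Grade 3 non-haematologic toxicity in Part 4, and does not say which applies

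*Combined protocol and SAP*

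**What the plan says.** Section 2.6.2 contains two rules for restarting TK216 after toxicity in Cohort 11.

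The first is a ladder that counts occurrences and names no event type. At the first event: "First occurrence, wait for the AE to decrease to ≤ Grade 2 and then resume TK216 at same dose and schedule". At the next: "Second or subsequent occurrence of AE- hold the dose until AE ≤ Grade 2, and then reduce TK216 daily dose to 145 mg/m²/day". If a further reduction is needed, the dose goes to 130 mg/m²/day.

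The second comes at the end of the section, under a heading for non-haematologic toxicity of Grade 3 or greater that is not clearly unrelated to TK216. It begins "Following any occurrence: hold TK216 until toxicities have resolved or improved to ≤ Grade 2 severity levels" and continues "then resume TK216 at same dose if event was a tolerable Grade 3", at the principal investigator's discretion. It then says "Reduce TK216 dose to one dose level lower (145 mg/m²/day, 130 mg/m²/day) than the current dose if event is Grade 3 or 4", and extends the reduction to intolerable Grade 2.

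Between the two stands general text. The investigator takes the decision to reduce. Two sentences say when a reduction may be unnecessary: one concerns supportive care ("Patients with toxicities that are manageable with supportive therapy may not require dose reductions"), the other toxicities up to Grade 3 that the investigator finds clinically tolerable. A third says "If unacceptable toxicity occurs in a patient, then that patient will be instructed to stop treatment".

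**The concern.** Both rules hold the drug until the event is Grade 2 or lower, so they differ only in the restart dose. The ladder looks at how often the event has happened; the non-haematologic rule looks at how severe and how tolerable it was. A first Grade 4 non-haematologic event meets the conditions of both, and a site that follows one rule departs from the other.

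What is at stake is patient safety and consistency between sites. The ladder, which a reader meets first, leads to a full-dose restart after a Grade 4 toxicity. The later rule requires a reduction. Part 4 gives a 28-day continuous infusion with no mandatory rest period (4.2.4.6) and enrols patients from age 8 (3.1), so the restart dose after such an event should have one answer.

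**Working it through.** No power, alpha or sample-size figure enters this point, and the plan states no figure to reproduce. The check is to apply both rules to the same event at the same current dose.

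**Inputs.** Starting dose 175 mg/m²/day, lower levels 145 and 130 mg/m²/day, 28-day cycle (all from 2.6.2).

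**Step 1: do the rules overlap?** The ladder waits for the event to fall to Grade 2 or lower, which presupposes an event of Grade 3 or more. It is not limited to haematologic events. Non-haematologic events of Grade 3 or greater therefore fall under both rules.

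**Step 2: restart dose under each rule (mg/m²/day).**

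| Non-haematologic event | Dose when it occurs | Ladder | Non-haematologic rule |
|---|---|---|---|
| First Grade 4 | 175 | 175 | 145 |
| First intolerable Grade 3 | 175 | 175 | 145 |
| First tolerable Grade 3 | 175 | 175 | 175 (discretion) |
| Second Grade 4 or intolerable Grade 3, still at 175 | 175 | 145 | 145 |
| Later Grade 4 or intolerable Grade 3, already at 145 | 145 | 130 | 130 |

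Only the first two rows differ. Placing intolerable Grade 3 under reduction is an interpretation: the rule lists Grade 3 both in its same-dose clause and in its reduction clause ("if event is Grade 3 or 4 or intolerable Grade 2 in severity"), and the two fit together only if the second means a Grade 3 that is not tolerable.

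**Step 3: size of the difference.**

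- Daily dose: 175 − 145 = 30 mg/m²/day.
- Relative to the full dose: 30 / 175 = 17.1%.
- Relative to the reduced dose: 30 / 145 = 20.7%.
- Over one uninterrupted cycle: 28 × 175 = 4,900 and 28 × 145 = 4,060 mg/m², a difference of 840 mg/m².

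The 840 is a ceiling for one cycle. The gap need not persist, because 2.6.2 lets the investigator raise the dose again once toxicity has resolved after a cycle at the lower level.

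**Step 4: is precedence stated anywhere?** Sections 2.6, 2.6.2, 2.6.3 and 2.6.4 contain no such sentence. Neither do the Cohort 11 schedule (4.2.4 and its subsections, 4.2.5) or the withdrawal criteria (4.2.8). The new-cycle criteria in 4.2.4.1, the restart checks in 4.2.4.6 and the discontinuation criterion in 4.2.8 decide whether a patient continues, not at what dose.

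**Step 5: comparison with Parts 1-3.** In 2.6.1.1 the same-dose-first ladder stands only under the neutropenia and thrombocytopenia headings, and the any-occurrence rule stands under the non-haematologic heading. There the two cannot collide. In Part 4 the ladder has lost its event headings, and the overlap follows from that.

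**The case against.** The best defence is that the specific rule governs the general one. The ladder names no event type. The later rule names non-haematologic toxicity of Grade 3 or greater and says that it applies at any occurrence, so the count is expressly irrelevant. Parts 1-3 point the same way. The investigator also decides on reductions, unacceptable toxicity ends treatment, and both rules hold the drug first. This makes the intended reading fairly clear and keeps the matter minor. It does not remove the error: 2.6.2 does not state the precedence, and the later rule attaches discretion only to a tolerable Grade 3. For Grade 4 it simply says to reduce. Discretion does not tell a site or a monitor which restart dose complies.

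Three stronger readings are tempting, and the documents do not support them.

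- A reader might infer a reverse conflict for a second tolerable Grade 3: 145 from the ladder bullet against 175 from the later rule. The general text of 2.6.2 answers this, because toxicities up to Grade 3 that the investigator finds tolerable may not need a reduction. Read as a whole, the section leaves that case to the investigator under both rules.
- A reader might count a second Grade 4 event as a further conflict, 145 against 130. That compares a patient still at 175 with one already reduced to 145, so it only carries the first divergence forward. At the same current dose both rules give the same next level.
- A reader might add intolerable Grade 2. The reduction clause mentions it, but the rule's heading starts at Grade 3 and the ladder waits for a fall to Grade 2 or lower. An overlap there is arguable at most.

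**Conclusion.** Wrong as written, but minor. For a first Grade 4 or intolerable Grade 3 non-haematologic toxicity at 175 mg/m²/day, 2.6.2 gives restart doses 30 mg/m²/day apart with no stated precedence. Later events and tolerable Grade 3 events add no separate conflict.

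This assumes that the patient is at 175 when the event occurs, with no earlier reduction and no increase to 200 under 2.6.3, and that an occurrence is counted for the same adverse event. The documents give no Part 4 toxicity rate, so the number of patients affected among about 21 is unknown.

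The effect is confined to dosing and safety. The primary endpoint, the exact test and the requirement of 4 responses in 21 evaluable patients (9.3) do not depend on which rule is followed.

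**What to change.** Three edits to 2.6.2, for confirmation by the sponsor's clinical team:

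1. State that the non-haematologic rule takes precedence over the occurrence ladder for all Grade 3 or greater non-haematologic toxicity not clearly unrelated to TK216.
2. In that rule's reduction clause, replace Grade 3 or 4 with Grade 4 or intolerable Grade 3, and keep intolerable Grade 2. These events then drop one level at the first occurrence, and a tolerable Grade 3 may resume at the same dose at the investigator's discretion.
3. Limit the ladder to adverse events covered neither by that rule nor by the neutropenia rules in 2.6.4. Neutropenia has to stay out of the ladder, because 2.6.4 sets its own thresholds: dosing can continue with G-CSF when the ANC falls below 1,000/mm³, and TK216 is held at 500/mm³ or lower.

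These edits do not settle what one level below 200 mg/m²/day is for a patient whose dose was increased; the sponsor could define that in the same amendment.

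The cost is a short wording change and, compared with following the ladder, slightly lower dose intensity after a first Grade 4 or intolerable Grade 3 event (145 instead of 175 mg/m²/day). Sample size, endpoint and decision rule do not change.
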